## 5.5. Demographics and Other Baseline Characteristics

Demographic data will be summarized descriptively and include:

- Age
- Sex
- Race
- Ethnic group

Listings of demographic data characteristics will be provided for each patient and summarized across the study population.

Baseline disease characteristics will be summarized descriptively and will include:

- CTCL Stage (IB, IIA)
- Number of previous CTCL treatments
- Time since original diagnosis to randomization
- Extent of disease (percent body area with lesions)
- Cumulative CAILS score for the 3 index lesions at Baseline
- Baseline VASitch score
- Baseline mSWAT
- Baseline Skindex-29 QoL score

## 5.6. Medical History

Medical history and current conditions will be presented and will be coded using the MedDRA (Medical Dictionary of Regulatory Activities, Version 10.1) system organ class (SOC) and preferred term.

The summary tables will include counts of patients in each term. If a patient experiences more than one medical history or current condition event that is coded to the same preferred term, the patient will be counted only once for that preferred term. Similarly, if a patient has more than one medical history or current condition within a SOC, the patient will be counted only once in that SOC.

Listings of medical history and current conditions will be provided.

## 5.7. Prior and Concomitant Medications

The World Health Organization Drug Dictionary (WHO Drug) will be used to classify prior and concomitant medications by therapeutic class and generic name based on ATC code level 3. Prior medication is defined as any medication taken prior to the first dose of the study medication. Concomitant medication is defined as any medication taken between the day of first dose of the study medication and the day of last study medication date + 14 days.

## 5.8. Interim Analysis

No Interim Analysis is planned.

## 6. OUTCOMES

### 6.1. Electrocardiograms

Changes in ECGs will be assessed by both continuous (analysis of central tendency) and categorical (shift tables) analyses.

#### 6.1.1 Analysis of Central Tendency

The mean and median response at Baseline and at each subsequent timepoint for each parameter will be assessed. Changes in response will be tracked and compared. The clinical meaningfulness of any alterations will be assessed.

Individual changes in each parameter will also be plotted and compared for evidence of trends.

#### 6.1.2 Categorical Analysis

Shift analysis will be conducted, evaluating the number of patients that meet the following criteria:

- Measured QT interval >500 ms
- QTc interval increased from baseline > 60 ms

The number of patients meeting these criteria at each timepoint will be tabulated.

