### 3.1 Primary

The primary endpoints for the study are:

Serial assessments of ECG (including QT interval and QT interval corrected for heart rate using both the Bazett's and Fridericia formulas) will be obtained at the same timepoints as serum hypericin samples as follows:

- a. Baseline prior to drug application
- b. Week 4, Session 2 obtained immediately before and 2 hours after the light session
- c. Week 6, Session 2 obtained immediately before the light session
- d. Week 8, Session 2 Light Session visit obtained immediately before and 2 hours after the light session
- e. Week 10 follow-up visit

Serial measurements of serum hypericin levels obtained at:

- f. Baseline prior to drug application
- g. Week 4, Session 2 obtained immediately before and 2 hours after the light session
- h. Week 6, Session 2 obtained immediately before the light session

- i. Week 8, Session 2 Drug Application visit immediately prior to the drug application
- j. Week 8, Session 2 Light Session visit obtained immediately before and 2 hours after the light session
- k. Week 10/End of Study during the follow-up visit

These levels will be correlated with amount of drug applied by the patient estimated by weighing the drug jars at each light session.

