### 10.2 Analysis of Safety

Listings of findings per patient will be provided. Average and median results for laboratory findings, vital signs, ECG findings and PK outcomes will be provided. Any significant outliers ( $>2x$  the standard deviation) will be highlighted. Listings of AEs within 48 hours of ointment application will be tabulated. Any serious or related AEs determined within 14 days of last drug application will be tabulated, in addition to any medications received during the 10-week period.

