### 4.1. Primary Endpoints

Serial assessments of ECG (including QT interval and QT interval corrected for heart rate using both the Bazett's and Fridericia's formulas) will be obtained at the same timepoints as serum hypericin samples as follows:

- Baseline prior to drug application
- Week 4, Session 2 obtained immediately before and 2 hours after the light session
- Week 6, Session 2 obtained immediately before the light session
- Week 8, Session 2 Light Session visit obtained immediately before and 2 hours after the light session
- End of Study during the follow-up visit

Serial measurements of serum hypericin levels obtained at the following timepoints will be correlated with the cumulative amount of drug applied by the patient estimated by weighing the drug jars at each light session:

- Baseline prior to drug application
- Week 4, Session 2 obtained immediately before and 2 hours after the light session
- Week 6, Session 2 obtained immediately before the light session
- Week 8, Session 2 Drug Application visit immediately prior to the drug application
- Week 8, Session 2 Light Session visit obtained immediately before and 2 hours after the light session
- End of Study during the follow-up visit

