### 4.4. Study Endpoint Definition

#### 4.4.1 Electrocardiograms (ECGs)

12-lead ECGs, including QT interval measurement, will be done at Baseline (prior to drug application), Week 4, Session 2 (immediately prior to and 2 hours after the light session), Week 6, Session 2 (immediately prior to the light session), Week 8, Session 2 Light Session Visit (immediately prior to and 2 hours after the light session), and at the End of Study visit. ECGs will be interpreted by site personnel trained in the evaluation of ECGs for any interval changes.

QT intervals will be measured on each ECG. Heart rate corrected QT intervals will be calculated using the following 2 standard correction equations:

*Bazett's Formula:*

$$QT_{cB} = QT_m / \text{square root of RR}$$

Where  $QT_{cB}$  represents the Bazett's corrected QT interval,  $QT_m$  is the measured QT interval, and RR is the time interval between 2 consecutive QRS complexes in seconds.

*Fridericia's Formula:*

$$QT_{cFri} = QT_m / \text{cube root of RR}$$

Where  $QT_{cFri}$  represents the Fridericia's corrected QT interval,  $QT_m$  is the measured QT interval, and RR is the time interval between 2 consecutive QRS complexes in seconds.

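### SAP 6.1.2 puts its only absolute QT limit (500 ms) on the uncorrected interval, so the count can miss patients with QTc above 500 ms at heart rates above 60 bpm and include patients with QTc below 500 ms at rates below 60 bpm

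*SAP*

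**What the plan says.** Protocol 3.1 and SAP 4.1 define the primary ECG endpoint as serial ECG assessments, in the SAP's words "including QT interval and QT interval corrected for heart rate using both the Bazett's and Fridericia's formulas".

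SAP 4.4.1 gives the two corrections. In each, the term QTm "is the measured QT interval, and RR is the time interval between 2 consecutive QRS complexes in seconds". The measured QT is therefore the uncorrected interval, and QTcB and QTcF are calculated from it.

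SAP 6.1 sets out the ECG analysis: "Changes in ECGs will be assessed by both continuous (analysis of central tendency) and categorical (shift tables) analyses". The categorical part, section 6.1.2, has two criteria, with the number of patients meeting them tabulated at each timepoint:

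- "Measured QT interval >500 ms"
- "QTc interval increased from baseline > 60 ms"

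The first names the measured QT and the second names QTc, so the first cannot be read as a limit on QTc. The second does not say which correction applies. No other section of either document sets an absolute limit on QTcB or QTcF.

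**The concern.** The 500 ms line is the only place where the plan asks whether any patient's repolarisation interval exceeded a fixed value. Because it uses the uncorrected interval, its answer depends on heart rate as well as on repolarisation. Above 60 bpm it is more lenient than the same limit on QTc; below 60 bpm it is stricter.

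At stake is one of the two planned analyses of a primary objective. About 6 patients are planned, so one patient wrongly left out or wrongly included moves the count by one in six. A row showing zero patients above 500 ms could be quoted as reassurance although a patient's corrected interval had passed 500 ms by both of the plan's own formulas.

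**Working it through.** **Inputs.** From SAP 4.4.1, with RR in seconds: QTcB = QT / RR^(1/2) and QTcF = QT / RR^(1/3), where RR = 60 / heart rate. From SAP 6.1.2: the 500 ms and 60 ms limits. The documents give no expected heart rate or baseline QTc, so the rates and QT values below are illustrative assumptions. The plan states no figure of its own to reproduce.

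**Step 1: measured QT at which QTc equals 500 ms.** Solving gives QT = 500 × RR^(1/3) for Fridericia and QT = 500 × RR^(1/2) for Bazett.

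| Heart rate (bpm) | RR (s) | Fridericia (ms) | Bazett (ms) | Effect on the >500 ms count |
|---|---|---|---|---|
| 50 | 1.2000 | 531.3 | 547.7 | QT from 500 up to these values is counted; QTc is below 500 |
| 55 | 1.0909 | 514.7 | 522.2 | as at 50 bpm |
| 60 | 1.0000 | 500.0 | 500.0 | the two limits coincide |
| 65 | 0.9231 | 486.8 | 480.4 | QT from these values up to 500 is not counted; QTc is above 500 |
| 75 | 0.8000 | 464.2 | 447.2 | as at 65 bpm |
| 90 | 0.6667 | 436.8 | 408.2 | as at 65 bpm |

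The band of disagreement widens as heart rate moves away from 60 bpm.

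**Step 2: one patient.** Take a measured QT of 480 ms at 75 bpm.

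- QTcF = 480 / 0.8^(1/3) = 517.1 ms.
- QTcB = 480 / 0.8^(1/2) = 536.7 ms.
- Both exceed 500 ms, but the measured QT does not, so the patient is not counted on the first criterion.
- The second criterion is met only if baseline QTcF was below 517.1 − 60 = 457.1 ms, or baseline QTcB below 536.7 − 60 = 476.7 ms.

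**Step 3: can a patient escape both criteria?** Hold heart rate at 75 bpm and let measured QT rise from 430 to 480 ms.

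- QTcF goes from 463.2 to 517.1 ms, a rise of 53.9 ms.
- QTcB goes from 480.8 to 536.7 ms, a rise of 55.9 ms.

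Both corrected values cross 500 ms. Neither rise exceeds 60 ms and the measured QT stays below 500 ms, so the categorical table shows no event.

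**Step 4: does the formula matter for the 60 ms criterion?** Assume baseline QTc of 400 ms at 60 bpm (the same under both formulas) and follow-up at 80 bpm, so RR = 0.75.

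- QTcB / QTcF = 0.75^(−1/6) = 1.0491.
- When QTcB reaches 460 ms, QTcF is 460 / 1.0491 = 438.5 ms.
- Bazett has then risen 60 ms and Fridericia 38.5 ms, so the two formulas can give different counts.

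**Step 5: does another rule supply an absolute check?** Protocol 10.2 states "Average and median results for laboratory findings, vital signs, ECG findings and PK outcomes will be provided. Any significant outliers", meaning values beyond twice the standard deviation, are to be highlighted. That rule is relative. Among n values the largest possible deviation from the mean is (n − 1)/√n sample SDs. If the SD is taken per timepoint, this is 5/√6 = 2.04 for 6 patients, 4/√5 = 1.79 for 5, and 7/√8 = 2.47 for the replacement ceiling of 8 in Protocol 5.4. With 6 patients the flag can barely fire; with 5 it cannot.

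**The case against.** The strongest reply is that the objective concerns ECG changes, and the change criterion already uses QTc. A patient who starts at or below 440 ms and passes 500 ms has risen by more than 60 ms on that formula and is counted. Only patients with baseline QTc above 440 ms can pass 500 ms unnoticed by both lines, and the documents do not show that any such patient will be enrolled. This bound is correct and limits the problem. It does not remove it: step 3 gives a patient whom both lines miss under both formulas, and neither document sets an entry limit on QTc.

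Second, the endpoint names QT as well as QTc, so one criterion on each contradicts nothing, and the first line is accurate as a count of measured QT. That is fair. The defect is the missing absolute QTc line; retaining the measured-QT line does no harm.

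Third, the study is small and exploratory. Six patients with seven ECGs each give 42 records, no decision rule depends on the count, trained site staff interpret every ECG, per-patient listings are planned, and under SAP 6.1.1 "Individual changes in each parameter will also be plotted and compared for evidence of trends". A high QTc would be visible there. This stands as a limit on the consequence: no data are lost. It does not make the tabulated count informative about QTc, because none of those outputs applies an absolute QTc limit.

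Fourth, the outlier argument depends on how the SD is taken and on n, and at 6 patients a flag remains just possible. It is a side point, and the conclusion does not depend on it.

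Finally, reading the 60 ms criterion as applying to both formulas is natural. That part is a wording gap and would not justify a comment alone.

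**Conclusion.** The concern holds and should be fixed. The direction of the error and the crossover at 60 bpm follow from the SAP's own formulas and need no outside figure. The size depends on heart rate. For omission, the Fridericia band is about 13 ms wide at 65 bpm (487 to 500), 36 ms at 75 bpm (464 to 500) and 63 ms at 90 bpm (437 to 500), and the Bazett bands are wider. For over-counting, it is about 15 ms at 55 bpm (500 to 515) and 31 ms at 50 bpm (500 to 531) for Fridericia. How many patients would fall in these bands cannot be derived from the documents. The effect is limited to the >500 ms count within one of the two primary ECG analyses; the means, medians, plots and listings of QTc are unaffected.

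**What to change.** In SAP 6.1.2:

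- Add QTc >500 ms as the absolute criterion, tabulated separately for QTcF and QTcB at each timepoint.
- Keep the measured QT >500 ms row as supplementary.
- State that the QTc rise of more than 60 ms is also tabulated separately for QTcF and QTcB.

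The cost is a few words in the SAP and one table shell. Both corrected values are already to be calculated for every ECG, so no new data or procedures are needed. If the SAP is already signed, its Introduction allows deviations that are described and justified in the study report, and the extra rows can be added that way.

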### 6.2. Hypericin blood concentrations

Hypericin blood calculations will be summarized as the mean, standard deviation and range of blood concentrations for each timepoint. A regression between cumulative drug application and measured blood concentration per visit (average result where samples were collected before and after light collection) will be conducted excluding the End of Study sample, if at least 50% of samples had detectable levels of circulating hypericin.

Changes in blood concentration over time will be described for each individual subject to assess the potential for accumulation.

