### Figure 1: Hypericin Blood Levels in Minipigs

Each line represents a single animal. Healthy male and female Göttingen mini-pigs received HyBryte applied to 10% BSA every second day. Most animals were below detection limit on Day 1. After 6 doses, healthy animals receiving no light treatment had less than 0.5 ng/ml hypericin in their blood stream, while healthy animals receiving 6 treatments HyBryte + 8 J/cm^2 light treatment 24 hours after drug application and occlusion, had less than 0.3 ng/mL hypericin. Similarly, animals receiving 5 treatments of HyBryte and 10 or 12 J/cm^2 light treatment had less than 0.3 ng/mL hypericin.

As seen, all hypericin levels were low and well below the lower limit of detection of the original assay. While systemic hypericin levels were barely detectable (LLOQ <0.05 ng/mL) after the first administration, this appeared to increase after 5 or 6 doses, with the highest detectable levels seen in animals receiving ointment only with no light sessions. Since very low levels were seen, it was determined that a small study of patients with

CTCL would provide more information about the PK of the topical drug over time (using the more sensitive assay) and allow contemporaneous assessment of ECG readings.

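### The SAP 6.2 regression of hypericin level on cumulative drug pools samples taken at different times after application, so its slope does not measure how level relates to amount applied

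*SAP*

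**What the plan says.** SAP 4.1 lists the serum hypericin measurements as a primary endpoint that "will be correlated with the cumulative amount of drug applied by the patient estimated by weighing the drug jars at each light session". SAP 6.2 turns this into a regression that uses one value per visit, "measured blood concentration per visit (average result where samples were collected before and after light collection"). It "will be conducted excluding the End of Study sample, if at least 50% of samples had detectable levels of circulating hypericin".

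The sampling times come from SAP 4.1 and 4.4.2. In order of cumulative applications, if all are made, the points are:

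- 0 applications: "Baseline prior to drug application".
- 8 applications: "Week 4, Session 2 obtained immediately before and 2 hours after the light session", so these two samples are averaged.
- 12 applications: "Week 6, Session 2 obtained immediately before the light session", a single sample.
- 15 applications: "Week 8, Session 2 Drug Application visit immediately prior to the drug application", a single sample before application 16.
- 16 applications: the Week 8 Light Session visit, again the average of a pre-light and a post-light sample.

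Baseline is not excluded. Neither section adds a term for time since application or for type of sample. SAP 6.2 also plans summaries at each timepoint and a description of each subject's course over time.

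**The concern.** A light session follows application by 18 to 24 h, so the pre-light samples share one place in the dosing interval. The sample before application 16 does not. Treatments must be at least 2 calendar days apart, so it falls at least about 48 h after application 15, where the level should be lower. It also sits at nearly the largest value of the predictor. A low reading there lowers the slope whatever the true relation between amount and level.

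Baseline acts in the opposite direction: zero drug and essentially zero concentration pull the line upward. The fitted slope then mainly reflects which kinds of sample were pooled. This is the only planned analysis that links hypericin level to amount applied, and about six patients are planned, each contributing the same systematic pattern.

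**Working it through.** The documents state no slope to reproduce, so the check asks what the planned fit returns when like-timed levels are flat or nearly so.

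**Inputs.** Cumulative applications are 0, 8, 12, 15 and 16 (SAP 4.1), taken as equal amounts. The pre-light sample is at 21 h, the middle of 18-24 h (SAP 3). The terminal half-life is 24.2 to 83.7 h (Protocol Table 1, oral and intravenous dosing). Spacing is 48 h (about the minimum) or 84 h (even twice-weekly dosing). Half-life after topical use, exact spacing and absorption complete by 21 h are assumptions.

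**Trough.** As a fraction of the pre-light level L, r = 2^(-(spacing - 21)/half-life).

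- 48 h: 2^(-27/24.2) = 0.46 to 2^(-27/83.7) = 0.80.
- 84 h: 2^(-63/24.2) = 0.165 to 2^(-63/83.7) = 0.59.

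**Averaging.** Protocol Table 4 gives light sessions of about 11 to 54 minutes, so the post-light sample is about 2.2 to 2.9 h after the pre-light one. The post/pre ratio is 2^(-2.9/24.2) = 0.92 to 2^(-2.2/83.7) = 0.98. Averaging therefore moves a value by at most (1 - 0.92)/2 = 4%.

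**Slope with Baseline kept.** Set L = 1 and Baseline = 0. The mean of x is 10.2 and Sxx = 168.8.

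- Slope = (-2.2 + 1.8 + 4.8r + 5.8)/168.8 = (5.4 + 4.8r)/168.8, which is positive for every r from 0 to 1.
- Without the trough (x = 0, 8, 12, 16; Sxx = 140), slope = (-1 + 3 + 7)/140 = 0.064.
- With r = 1 the five-point slope would be 10.2/168.8 = 0.060. So about 6 percentage points of the reductions below come from adding a point at 15, and the rest from its low level.

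**Slope with Baseline left out.** The mean of x is 12.75 and Sxx = 38.75.

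- Slope = (-4.75 - 0.75 + 2.25r + 3.25)/38.75 = -2.25(1 - r)/38.75, which is negative for every r below 1.

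**Full calculation.** One-compartment superposition of equal doses, with post-light samples at 23.5 h and averaging as planned. Changes are in the fitted level from 8 to 16 applications.

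| Spacing, half-life | r | Slope, Baseline in (units of L) | Cut from 0.064 | Change, Baseline in | Change, Baseline out | Change, three pre-light samples |
|---|---|---|---|---|---|---|
| 48 h, 24.2 h | 0.46 | 0.044 | 31% | +61% | -24% | 0% |
| 48 h, 83.7 h | 0.80 | 0.055 | 15% | +70% | -5% | +4% |
| 84 h, 24.2 h | 0.165 | 0.036 | 44% | +53% | -38% | 0% |
| 84 h, 83.7 h | 0.59 | 0.049 | 24% | +64% | -18% | 0% |

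The last column is what a fit to like-timed samples returns. Neither pooled fit comes close to it, and the two pooled fits have opposite signs.

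If a Baseline result below the 0.05 ng/mL detection level is entered as 0.05, as the convention in SAP 5.4 would suggest, the slope with Baseline kept remains positive in every case tried (L from 0.06 to 1 ng/mL).

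**The case against.** **A falling line.** A reader might infer that the planned regression will slope downward and suggest no increase with more drug. The documents do not support this. SAP 6.2 excludes only End of Study, and SAP 4.1 names Baseline among the correlated samples. Under that rule the line rises even when like-timed levels are flat. Nor is a fall certain with Baseline left out, once patients apply different amounts. In simulations of six patients with assumed variability (30% residual, 50% between patients in level, 0-60% in amount applied), the slope without Baseline was negative in 59-99% of runs when level did not depend on amount, and in 5-99% when it was proportional to amount.

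**Averaging.** A reader might also treat averaging across the light session as a main fault, because the Protocol reports the "highest detectable levels seen in animals receiving ointment only with no light sessions". That comparison sets animals never lit against animals lit repeatedly, and the text gives only upper bounds (below 0.5 and below 0.3 ng/mL). It does not show a change over about two hours. On kinetics alone, averaging is minor.

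**Kinetics.** The half-lives come from systemic dosing, and Protocol 1.1.2 itself says the parenteral trials do not carry over directly to the ointment. Slower uptake from skin would raise the trough. With applications 72/96 h apart and an absorption half-life of 12 h rather than 2 h, the ratio rises from 0.22-0.61 to 0.38-0.73. The distortion shrinks but keeps its direction.

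**Weight.** The study is exploratory, the regression runs only if at least half the samples are detectable, and no test or decision rests on the slope. The timepoint summaries and individual descriptions keep the sample types apart, and SAP 6.2 assigns accumulation to the individual descriptions. All of this stands and limits the consequence. None of it makes the slope interpretable, and neither of those summaries relates level to amount applied.

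**Conclusion.** The point holds as a defect in how the regression is specified. Pooling a pre-application trough with samples near 24 h, without a term for time since application, lowers the slope relative to like-timed samples. Under the stated half-life and spacing assumptions, the reduction is about 15-44% with Baseline kept, as the SAP implies. With Baseline left out and equal doses, there is a spurious fall of about 5-38% while the like-timed levels change by 0% to +4%. In that setting the sign is set by the handling of Baseline, not by the drug.

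The direction of the trough effect needs only that levels decline between about 21 h and the next application. Its size rests on kinetics that the documents do not give for topical use. Averaging contributes at most about 4% unless light itself changes blood levels, which the documents do not quantify in humans. The wording should be changed, but the point does not undermine the other hypericin summaries.

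**What to change.** In SAP 6.2:

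1. Run the regression on the pre-light samples at Week 4, Week 6 and the Week 8 Light Session visit, without averaging in the post-light values.
2. State explicitly that Baseline is left out of this fit. Dropping the trough alone is not enough: with Baseline kept and like-timed levels flat, the slope is still about 0.064 of the pre-light level per application.
3. Report the Week 8 pre-application trough as a separate descriptive result.
4. Report the within-patient post-light minus pre-light difference at Weeks 4 and 8 descriptively, so that any effect of light is visible.

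This changes SAP wording only, and SAP 4.1 and 4.4.2 already schedule every sample. The list in Protocol 6.3 omits the Week 8 pre-light sample, which Protocol 3.1, Protocol 5.3.9 and Protocol Table 3 include. That list should be reconciled, because the fit depends on this sample. The cost is three on-treatment points per patient instead of four.

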## INTRODUCTION

This statistical analysis plan (SAP) provides a more technical and detailed elaboration of the statistical analyses of safety, pharmacokinetics (PK), and lesion response as outlined and/or specified in Amendment 1 of the final study protocol dated 22 April 2022.

Any deviations from this SAP will be described and justified in the Clinical Study Report (CSR). The preparation of this SAP has been based on International Conference on Harmonisation (ICH) E3 and E9 guidelines [1, 2]. If the protocol is subsequently amended, this SAP will be amended as well, if warranted. Should the SAP and the protocol be inconsistent with respect to the planned analyses, the language of the SAP prevails.

All data analyses and generation of TFLs will be performed using SAS® version 9.4 or higher. The SAP will be finalized and signed off prior to locking the database and subsequent unblinding of treatment arm assignments.

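### The 50%-detectable condition on the hypericin level-versus-amount regression has no defined denominator; read literally it counts pre-drug Baseline samples, and no level-versus-amount analysis replaces the regression if the condition fails

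*SAP*

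**What the plan says.** Both documents place the relation between hypericin level and amount of drug under the primary endpoints. Protocol 3.1 states it without condition: "These levels will be correlated with amount of drug applied by the patient". SAP 4.1 says that the serial levels "will be correlated with the cumulative amount of drug applied by the patient estimated by weighing the drug jars at each light session", again without condition.

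SAP 6.2 turns this into a regression of blood concentration on cumulative drug application, per visit, averaging the samples taken before and after light. It then adds a condition. In the same sentence it leaves out the End of Study sample and runs the regression only "if at least 50% of samples had detectable levels of circulating hypericin". Nothing in SAP 6.2 or elsewhere defines which samples make up the 50%, or whether a visit average counts as one sample.

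The first sample in the SAP 4.1 hypericin list is "Baseline prior to drug application". It is not excluded from the regression or from the condition. On inconsistencies over planned analyses, the SAP Introduction says that "the language of the SAP prevails", so the conditional version governs over the protocol.

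**The concern.** A Baseline sample is taken before the first application, so it can only count against the condition. If it is in the denominator, the share of on-treatment samples that must be detectable is higher than the stated 50%. The regression could then be dropped although more than half of the samples that could show absorption did show it.

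A mixture of detectable and undetectable on-treatment results is also the situation in which the amount applied might help to explain who absorbs drug. Dropping the analysis there loses the information that the endpoint was meant to give. Because the denominator is undefined in an open-label study, the choice that decides whether the analysis runs could be made after the concentrations are known.

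**Working it through.** The documents give no sample-size or power figure to reproduce (SAP 5.1 calls the sample size arbitrary). The check is a count.

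**Inputs**
- Hypericin samples per patient (SAP 4.1 and 4.4.2): Baseline 1; Week 4 Session 2, 2 ("Week 4, Session 2 obtained immediately before and 2 hours after the light session"); Week 6 Session 2, 1; Week 8 drug application visit, 1; Week 8 light session visit, 2; End of Study, 1. Total 8, of which 2 + 1 + 1 + 2 = 6 are on treatment.
- Patients: about 6 (Protocol 5.1); up to 8 with replacement (Protocol 5.4).
- Assumptions: complete sampling; Baseline undetectable; End of Study undetectable where it is counted.

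**Formula.** Detections needed = 0.5 × denominator. Effective requirement = detections needed ÷ on-treatment samples.

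**Six patients (6 × 6 = 36 on-treatment samples)**

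| Denominator | Total | Detections needed | Share of the 36 | More than half detectable, yet dropped |
|---|---|---|---|---|
| On-treatment only | 36 | 18 | 50.0% | never |
| On-treatment + Baseline | 42 | 21 | 58.3% | 19 or 20 of 36 |
| On-treatment + Baseline + End of Study | 48 | 24 | 66.7% | 19 to 23 of 36 |

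Check of the middle row: 19/36 = 52.8% but 19/42 = 45.2%; 20/36 = 55.6% but 20/42 = 47.6%; 21/42 = 50.0%, so the regression runs.

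**Sensitivity**
- Eight patients: 28 of 48 (58.3%) and 32 of 48 (66.7%), so the requirements are unchanged.
- The Protocol 6.3 list omits the Week 8 pre-light sample, leaving 5 on-treatment samples per patient. For six patients the requirements become 18 of 30 (60.0%) and 21 of 30 (70.0%).
- If the unit is the visit average, with Baseline in and End of Study out: 15 of 24 visits (62.5%) if the two Week 8 visits are separate, or 12 of 18 (66.7%) if they are merged.

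**How often it could matter.** The documents give no on-treatment detection rate in patients with the 0.05 ng/mL assay, so the rate p is assumed. With X ~ Binomial(36, p) and independent samples, the chance that more than half are detectable and the regression is still dropped is:

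| p | Baseline counted: P(19 ≤ X ≤ 20) | Baseline and End of Study counted: P(19 ≤ X ≤ 23) |
|---|---|---|
| 0.50 | 0.231 | 0.401 |
| 0.55 | 0.260 | 0.563 |
| 0.60 | 0.205 | 0.593 |
| 0.65 | 0.110 | 0.461 |
| 0.70 | 0.038 | 0.254 |

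Samples from one patient are unlikely to be independent, so these figures are only illustrative.

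**What remains if the condition fails.** SAP 6.2 still gives mean, SD and range by timepoint and a description of each patient's course over time. SAP 6.3 lists changes in jar weight. None of these outputs sets level against amount.

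**The case against.** The strongest reply is that the SAP does not say that Baseline counts. An on-treatment denominator is open, and it removes the problem entirely. That stands: the denominator is undefined rather than plainly wrong. But nothing in SAP 6.2 points to that reading, and naming End of Study while staying silent on Baseline points the other way.

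Counting Baseline could also be deliberate. It is a zero-dose point that the SAP leaves in the regression, and a limit on non-detects among the regression data would naturally include it. That is possible, but the SAP does not say so.

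A reader might infer that the requirement is two-thirds. The documents do not support that as the plain reading. The End of Study exclusion sits directly beside the condition and can be taken to govern it, and 66.7% further needs every End of Study sample to be undetectable. Those samples are post-dose; only Baseline cannot contain study drug.

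A reader might also infer that the regression is generally lost whenever just over half of the on-treatment samples are detectable. With End of Study out, this happens at two counts only, 19 and 20 of 36.

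Nor do the minipig data show that patients will sit near the detection limit. "Most animals were below detection limit on Day 1" describes the first dose, whereas the first on-treatment sample here follows about eight applications (4 weeks × 2). The stated bounds after 5 or 6 doses, 0.3 and 0.5 ng/mL, are 6 and 10 times the 0.05 ng/mL limit. They are upper bounds, so they do not settle the detection rate either way.

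Finally, the study is exploratory, no decision rests on this regression, and with about 6 patients a reader could compare the listings by eye. That limits the consequence, but a listing of jar weights beside a separate summary of levels is not the correlation that both endpoint sections name.

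**Conclusion.** The point holds in a limited form. The 50% condition lacks a defined denominator and unit. On the literal reading, with Baseline counted and End of Study excluded, it requires 21 of 36 on-treatment samples (58.3%), so the regression can be dropped with 19 or 20 of 36 detectable. The 66.7% figure applies only if End of Study is also counted and entirely undetectable. Under an on-treatment reading there is no discrepancy. These figures assume 6 patients with complete sampling; the two percentages are the same with 8.

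The more lasting weakness is that, when the condition fails under any reading, the SAP has no analysis relating level to amount, although Protocol 3.1 lists that relation under the primary endpoints without condition. This should be corrected. It does not threaten the study, because the regression is exploratory and the concentrations are reported in any case. How likely the condition is to decide the matter cannot be judged from the documents.

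**What to change.** In SAP 6.2:

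1. Compute the 50% from on-treatment samples only, with Baseline and End of Study both out.
2. State whether the unit is the individual sample or the visit average.
3. State separately whether Baseline stays in the regression as a zero-dose point.
4. If the condition is not met, still report a descriptive rank correlation of level with cumulative amount, with undetectable values tied at the lowest rank, and tabulate cumulative grams applied for detectable versus undetectable results.

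With the first change, and the sample as unit, the condition is met at 18 of 36 for 6 patients (24 of 48 for 8), and no case with more than half of on-treatment samples detectable is dropped.

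The cost is a few sentences of SAP text and one table, with no new data. The drawback is that the fallback will be imprecise with about 6 patients and repeated samples per patient, so it must be labelled descriptive.
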